2.5.2 Statistical hypothesis, model, and method of analysis

For the primary analysis, the following hypothesis testing will be performed:

$$H_{01}: p_{sec} = p_{nbUVB} \text{ versus } H_{A1}: p_{sec} > p_{nbUVB}$$

where p_{sec} and p_{nbUVB} are the proportion of PASI 90 responders in the secukinumab 300 mg s.c. (Arm A1) and nb-UVB (Arm B1) groups, respectively.

The primary analysis method for PASI 90 response at Week 52 will use a logistic regression model with treatment as an explanatory variable and significant covariates among Baseline PASI score, age, and BMI. The best subset of the significant covariates will be selected using a forward selection method based on the likelihood ratio test. Interaction terms with treatment will also be considered, if significant, among the best subset of selected covariates and the treatment term.

Statistical significance will be evaluated at a 1-sided alpha level of 0.025. The estimated adjusted odds ratio for Arm A1 versus Arm B1 will be displayed along with the associated 2-sided 95% confidence interval (equivalent to the 1-sided 97.5% confidence interval) and p-value.

If there are issues related to the convergence of the logistic regression model, the above hypothesis will be tested using a 1- sided Wald test.

The primary analysis is not expected to be influenced by the use of topical treatment within the first 4 weeks since, any effect will be worn off by Week 52.

The detailed testing strategy including the primary endpoint analysis is provided in Section [2.6.2](#)

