2.5.4 Supportive analyses

Sensitivity analysis will be performed on the primary analysis method for PASI 90 response at Week 52 by repeating the logistic regression model with treatment as an explanatory variable and all three covariates Baseline PASI score, age, and BMI. Interaction terms with treatment also will be considered.

If logistic regression model does not converge the following steps will be performed:

1. Run the PROC GENMOD procedure with EXACT statement;
2. If convergence not reached, remove the covariates from the model one by one until convergence is reached; start with continuous covariates (i.e., baseline BMI by replacing with BMI stratum (< 25, 25-< 30, >= 30), and then baselines PASI score), followed by removing categorical covariates (i.e., BMI stratum etc.);
3. If convergence not reached, perform 1 sided Wald test.

It should be noted that this model might not converge if response rates are too low.

The impact of missing data on the analysis results of PASI 90 at Week 52 will be assessed as well by repeating the logistic regression model using different ways to handle missing data.

- Non-responder imputation
- Tipping point analysis
- Last observation carry forward (LOCF)

A non-responder imputation will be used as a supportive analysis of the primary variable using logistic regression (forward selection method) as described in primary analysis method. In this analysis, a missing value of PASI 90 response at Week 52 will be imputed with non - response regardless of the reason for missing data (e.g., premature study discontinuation, missed visit, administrative issues).

Assuming significance is shown for the primary analysis using non-responder imputation, the tipping point analysis will investigate if, and at which point, significance is not achieved anymore as subjects imputed as non-responders are increasingly reclassified as responders independently for each treatment group.

For PASI 90 response, missing values will be replaced by LOCF. Baseline values will not be carried forward. Similar analysis will be performed using logistic regression (forward selection method) as described in primary analysis method.

An additional analysis might be considered including Week 52 assessments performed later than per visit windowing due to covid.

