2.15.9 Investigators global assessment mod 2011 score and response over time

Treatment Arm A1 will be compared with Arm B1 based on IGA mod 2011 0/1 responses at Week 104 using a similar logistic regression model as described in [Section 2.7.1](#). Analysis will be performed on FUP efficacy analysis set on observed data only.

IGA mod 2011 score will be summarized descriptively, using number and percentages by visits. Confidence intervals for response rates will be derived as well based on the score method including continuity correction ([Newcombe 1998](#)). Graphical presentation will be performed for responders (%) at each scheduled visit from observed data using scatter plot.

IGA mod 2011 score will be summarized descriptively, using number and percentages by visits. Confidence intervals for response rates will be derived as well based on the score method including continuity correction ([Newcombe 1998](#)).

[REDACTED]

3 Sample size calculation

The sample size calculation is performed for the primary endpoint (proportion of PASI 90 responders at Week 52) and the key secondary endpoint (proportion of all randomized subjects who achieve PASI 90 response at Week 104). The selected total sample size is 160 subjects, such that 80 subjects are randomized in each arm.

The sample size calculation based on the proportion of PASI 90 responders at Week 104 was performed using PASS 11.

The power calculations for the primary endpoint are based on the asymptotic Wald test to compare secukinumab 300 mg s.c. versus nb-UVB using the hierarchical method to adjust for multiplicity. Based on data (unpublished) and experiences from recent studies, it is assumed that the proportion of PASI 90 responders at Week 52 will be around 70% after early treatment with secukinumab 300 mg s.c. (Arm A1) and around 35% after 1 or 2 cycles of nb-UVB treatment (Arm B1). With assumed approximate 0% dropout rate in Arm A1, and 20% in Arm B1 until Week 52 due to lack of efficacy or AEs (considered non-responders), the response rate would change to 70% and 28%, respectively. Assuming an absolute difference of 42% in the proportion of subjects achieving PASI 90 at Week 52, the sample size of 80 subjects in each arm would provide 99.9% power at the 1-sided significance level of 0.025 using asymptotic Wald test for equality of proportions (using PASS 11).

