Programming notes:

- The SAS procedure MIANALYZE expects a variable called “_IMPUTATION_” which is generated by the MI procedure. It might be needed to set the SAS option “VALIDVARNAM=UPCASE” temporarily in the program before the MI call, this option should be reset after the MIANALYZE call to VALIDVARNAM=V6.
- In case there are none missing in one treatment group, the MI procedure does not impute any values. In this case the corresponding data need to be imputed manually outside PROC MI and added to the dataset <impdata>.

The imputed data are saved in data set <impdata>. The outcomes of interest, i.e. the PASI 90 response will be calculated, e.g. as follows:

```
DATA <impdata2>;  
SET <impdata>;  
IF <change from Baseline PASI week primary endpoint>/<Baseline PASI <= -0.90 THEN <PASI 90 response> =1;  
ELSE <PASI 90 response>=0;
```

The treatment differences for each imputed data set will then be evaluated by means of a logistic regression model with treatment as an explanatory variable and significant covariates among Baseline PASI score, age, and BMI, and interaction terms with treatment as covariates, as described in [Section 2.5.2](#).

This analysis will be done by `_IMPUTATION_` for each pairwise comparison to the nb -UVB group. The data set should be sorted such that the nb-UVB group comes last. The model should be estimating response probability = 1 by using `DESECCENDING` option.

The `MIANALYZE` procedure expects the parameter estimate in the variables `ESTIMATE`, and the corresponding standard error in the variable `STDERR`. The standard error can be derived for the log(odds ratio). Based on the data set `Common RelRisks`, as described above, those can be programmed as

```
...  
IF value NE . AND value>0 THEN ESTIMATE=LOG(value);  
IF lowercl NE . AND value>0 THEN STDERR=LOG(lowercl/value)/-PROBIT(1-<alpha>/2);  
Effect="LogOR";  
...
```

The estimates and standard errors of the log(odds ratio) based on the 500 imputed data are then combined by applying Rubin's rules for multiple imputed data sets, see Little and Rubin (2002).

Programming notes:

- The variables `ESTIMATE` and `STDERR` in the input data set for the `MIANALYZE` procedure may not be missing. Records with missing values need to be deleted and the variable `_IMPUTATION_` needs to be renumbered and regenerated since for each bygroup the procedure expects consecutive numbers starting at 1.

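### The primary Week 52 odds ratio has no pre-specified covariate set, because covariates are chosen by significance within each of 500 imputed data sets before pooling

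*SAP*

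**What the plan says.** SAP 2.5.2, repeating protocol 9.4.2, takes baseline PASI, age and BMI as candidate covariates: "The best subset of the significant covariates will be selected using a forward selection method based on the likelihood ratio test". Treatment interactions are added if significant. No entry level is given. The result is judged by this rule: "Statistical significance will be evaluated at a 1-sided alpha level of 0.025".

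SAP 5.6.1 creates 500 imputed data sets and analyses each, by imputation number, with a "logistic regression model with treatment as an explanatory variable and significant covariates among Baseline PASI score, age, and BMI, and interaction terms with treatment", referring back to 2.5.2. The PROC LOGISTIC template carries the forward-selection option inside the call. It lists main effects only. The next step is pooling: "The estimates and standard errors of the log(odds ratio) based on the 500 imputed data are then combined by applying" Rubin's rules.

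SAP 2.5.4 plans a sensitivity analysis "repeating the logistic regression model with treatment as an explanatory variable and all three covariates Baseline PASI score, age, and BMI". Its next sentence adds that treatment interactions will be considered there too.

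For IGA 0/1 at Week 52, protocol 9.5.2 and SAP 2.7.1 use the same kind of selection, with baseline IGA in place of baseline PASI. Missing IGA responses are set to non-response.

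**The concern.** A selector driven by significance and run separately in each imputed data set need not choose the same terms each time. A covariate near the entry threshold will be in some fits and out of others.

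The odds ratio is non-collapsible: adjusting for a prognostic covariate changes the quantity estimated, even in a randomised trial. If an interaction is in the model, the treatment effect also depends on the covariate value at which it is read. Rubin's rules combine estimates of one common parameter, and here the plan does not say which parameter that is.

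What is at stake is the meaning of the headline adjusted odds ratio and its interval. A reader of the report could not say what the estimate is adjusted for, and the plan leaves that to the data.

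**Working it through.** **Inputs from the documents.** Sample size, SAP Section 3: "The selected total sample size is 160 subjects, such that 80 subjects are randomized in each arm". Attrition counted as non-response, same section: "With assumed approximate 0% dropout rate in Arm A1, and 20% in Arm B1 until Week 52". Rates: "the response rate would change to 70% and 28%, respectively". One-sided alpha 0.025; 500 imputations (SAP 5.6.1).

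**Inputs assumed.** The documents give neither the share of Week 52 values to be imputed nor the covariate effects. I take 5%, 10% and 20% imputed, covariate log odds ratios of about 0.2 to 0.4 per SD (and none), and entry at p < 0.05.

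**1. The plan's power figure.** SE = √(0.70×0.30/80 + 0.28×0.72/80) = √0.005145 = 0.0717. Then z = 0.42/0.0717 − 1.96 = 3.9, which gives power of 99.995% (99.99% with pooled variance). The stated 99.9% is reproduced and does not depend on this issue. The implied unadjusted odds ratio is (0.70/0.30)/(0.28/0.72) = 6.0.

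**2. Is one model fixed across imputations?** SAP 2.5.2 defines the model by selection. SAP 5.6.1 applies it to each imputed data set, and the selection option sits in the code. Nothing provides for selecting once on observed data, by majority vote or by a pooled test. The SAP never says outright that selection is repeated, but that is the natural reading and nothing contradicts it.

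**3. How often do models mix?** Simulations with 80 per arm and about 67 to 70% v 28% responders:

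| Run | Set-up | Imputed | Trials with more than one model |
|---|---|---|---|
| A | 400 trials, 12–15 imputations, interactions allowed | 5 / 10% | 58 / 76% |
| B | 40 trials per setting, 100 imputations by arm, interactions allowed | 5 / 10 / 20% | 53 / 68 / 90% |
| B0 | as B, no covariate effects | 5 / 10 / 20% | 38 / 55 / 65% |
| C | 1000 trials, 20 imputations, log odds ratios 0.4, 0.3, 0.2 per SD | 10% | 79% |
| D | 400 trials, main effects only | 10% | 75% |

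At 10% imputed with covariate effects, the mean of A to D is (76 + 68 + 79 + 75)/4 = 74.5%. One discordant imputation is enough to count as mixing. In run B the commonest model held 88 / 83 / 73% of imputations.

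In a further 25 trials at 10%, 13 had two or more models each holding at least 5% of imputations. Within those 13, the treatment log odds ratio differed between models by 0.15 on average and 0.34 at most, i.e. factors of e^0.15 = 1.16 and e^0.34 = 1.40.

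**4. How far does the pooled odds ratio move?** Differences at 10% imputed, median (95th percentile):

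| Comparison | Run A | Run C | Run D |
|---|---|---|---|
| Re-selection v fixed model | 3.5% (15%) | 3.5% (12.3%) | 3.1% (13%) |
| Re-selection v select once | – | 0.9% (8.8%) | 0.6% (8.5%) |
| Select once v fixed model | – | 4.1% (16.6%) | – |

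Selecting once, with no mixing at all, departs from the fixed model at least as far as re-selection does. The movement is therefore mainly an effect of selection. Against run A's mean standard error of 0.404, a 3.5% shift is ln(1.035)/0.404 = 0.09 standard errors, and a 15% shift is ln(1.15)/0.404 = 0.35.

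**5. Error rate and interval.**
- One-sided rejection under the null (run A, 800 trials): 2.9% with selection v 3.0% with the fixed model; simulation error √(0.03×0.97/800) = 0.6 points.
- Mean SE over empirical SD (run A): 0.404/0.423 = 0.955 with selection and 0.407/0.417 = 0.976 with the fixed model, shortfalls of 4.5% and 2.4%. The simulation error of an SD from 400 trials is 1/√(2×399) = 3.5%, so neither is distinguishable from zero.
- Coverage, selection v fixed: 93.6% v 93.7% (run C, about each estimator's own mean); 93.5% v 92.5% (run D).

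**The case against.** The strongest reply is that little changes in practice. The commonest model usually dominates, pooling across models moves the odds ratio by under 1% at the median, planned power is 99.9%, and a three-covariate analysis is already planned as a sensitivity analysis. All of this stands, and it limits the point to what the estimate means.

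A reader might go further in four ways that the material does not support:

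- **The interval is too narrow or the test too liberal.** Neither is shown (step 5). Rubin's between-imputation variance already includes the spread between models across imputations; only selection within a data set is left out.
- **Mixing of models is the main source of the shift.** The select-once comparison says otherwise.
- **Interactions will enter the pooled model.** The text of 2.5.2 and 5.6.1 allows this, but the template has main effects only and reports a least-squares-means contrast. As coded, none can enter. Text and code disagree and need reconciling.
- **IGA has the same pooling defect.** It does not: non-responder imputation leaves one data set. Only the significance-based choice of covariates is shared.

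It is also fair to say that forward selection is the protocol's own method, and that SAP 2.14.1 records a report already prepared for the Week 52 primary analysis. Replacing the model now would be a change after results in an open-label trial. That bears on how to fix the problem, not on whether it exists.

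**Conclusion.** The point holds in limited form. As written, the primary adjusted odds ratio for PASI 90 at Week 52 has no pre-specified covariate set and may average differently adjusted odds ratios. Mixing is likely rather than certain: with few imputed values or one dominant covariate, all 500 fits could agree.

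At an assumed 10% imputed and modest covariate effects, about three quarters of simulated trials mix models. The odds ratio departs from the fixed-covariate model by about 3% at the median and 12 to 15% at the 95th percentile, mostly because of selection. These sizes rest on an assumed missing rate, covariate effects and entry level, and on 12 to 100 imputations rather than 500. The test decision is very unlikely to change. SAP 2.6.2 and 2.6.3 carry a similar approach to Week 104; that was not simulated.

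**What to change.** **Primary model.** Define the Week 52 PASI 90 model as treatment, baseline PASI, age and BMI, without interactions, in every imputed data set, then pool. This is the SAP 2.5.4 model with its sentence on considering interactions removed; as it stands, 2.5.4 is not fully fixed either. It also removes a side problem: the template does not force treatment into the forward selection, while the programming notes delete records with missing estimates.

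**Supportive analyses.** Move forward selection and interactions here, with terms selected once and the entry level stated. Make the interaction text and the code template agree.

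**IGA.** Pre-specify treatment, baseline IGA, age and BMI. The reason is selection only, as there is no multiple imputation.

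**If the Week 52 primary analysis can no longer be replaced.** Report the fixed model beside it, labelled as such, with the frequency of each selected model across the 500 fits.

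**Cost.** A change to the analyses specified in protocol 9.4.2 and 9.5.2 as well as to the SAP, simpler code, and up to three covariate parameters that may carry no information.

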5.6.1.1 Logistic regression (Supportive analysis)

```
PROC GENMOD <option>;
CLASS <stratum> <treatment>;
MODEL <response> = <explanatory variables> / link=logit dist=bin type3;
ESTIMATE "OR. AIN 300 mg VS. nb_UVB" <treatment> 1 -1/exp;
ODS OUTPUT Estimates=Estimates;
RUN;
```

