6.4.1 Assessment of body surface area and psoriasis area severity index

The investigator or trained qualified designee will complete the PASI assessment as indicated in [Table 6-1](#), [Table 6-2](#), and [Table 6-3](#). Whenever possible, the same evaluator should perform this assessment at all visits.

The total BSA affected by plaque psoriasis will be estimated from the percentages of the affected areas, including head, trunk, upper limbs and lower limbs.

The following calculations will be done: each reported percentage will be multiplied by the factor that corresponds to the respective body region (head = 0.1, trunk = 0.3, upper limbs = 0.2, lower limbs = 0.4). The resulting 4 percentages will be added up to estimate the total BSA affected by plaque psoriasis.

A PASI score ([Fredriksson and Pettersson 1978](#), [Gottlieb et al 2005](#)) will be derived as indicated in [Table 6-4](#). The head, trunk, upper limbs and lower limbs will be assessed separately for erythema, thickening (plaque elevation, induration), and scaling (desquamation). The average degree of severity of each sign in each of the 4 body regions will be assigned a score of 0-4. The area covered by lesions on each body region will be estimated as a percentage of the total area of that particular body region. Further practical details to help with the assessment are provided below:

1. The neck is assessed as part of the head
2. The axillae and groin are assessed as part of the trunk
3. The buttocks are assessed as part of the lower limbs
4. When scoring the severity of erythema, scales should not be removed

Because the head and neck, upper limbs, trunk and lower limbs correspond to approximately 10%, 20%, 30% and 40% of the BSA, respectively, the PASI score is calculated using the formula:

$$\text{PASI} = 0.1(E_H + I_H + D_H)A_H + 0.2(E_U + I_U + D_U)A_U + 0.3(E_T + I_T + D_T)A_T + 0.4(E_L + I_L + D_L)A_L$$

The keys for the letters are provided in [Table 6-4](#).

PASI scores can range from a lower value of 0, corresponding to no signs of psoriasis, up to a theoretic maximum of 72.0.

The baseline value for the analysis of the PASI will be collected at baseline.

Patients require a total BSA of 10% or more affected by plaque psoriasis and a PASI score of 10 or more at screening and baseline to be eligible for this study.

Table 6-4 Psoriasis area severity index scoring system

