5.6 Statistical models

5.6.1 Primary analysis

For the primary analysis (at Week 52), the following hypothesis testing will be performed:

$$H_{01}: p_{sec} = p_{nbUVB} \text{ versus } H_{A1}: p_{sec} > p_{nbUVB}$$

where p_{sec} and p_{nbUVB} are the proportion of PASI 90 responders in the secukinumab 300 mg s.c. (Arm A1) and nb-UVB (Arm B) groups, respectively.

Model:

Forward selection method will be performed in order to select the subset of significant covariates from Baseline PASI score, age and BMI, and their interaction with treatment.

$\text{Logit}(\pi_i) = \beta_1 * \text{treatment} + \beta_2 * \text{Baseline PASI score} + \beta_3 * \text{age} + \beta_4 * \text{BMI} + \beta_5 * \text{Baseline PASI score} * \text{treatment} + \beta_6 * \text{age} * \text{treatment} + \beta_7 * \text{BMI} * \text{treatment} + \text{error}$

where π_i is the probability that the i th subject is PASI 90 responder given that i th subject receives x_j treatment, where treatment x_j is AIN if j is 1 and nb-UVB if j is 2.

SAS code:

Using the PROC LOGISTIC the estimates of treatment differences and corresponding adjusted odds ratio and 95% CI. For Primary , Additional secondary objective. And in Other section as applicable.

```
proc logistic data= <PASI_IGA> descending covout outest=betas;
  class TRT/param=glm;
  model RESPONDER (event='1')= <Baseline XXX> <Treatment> <Age> <BMI>
    / selection=forward

    details
    lackfit;
  lsmeans trt/diff cl exp ODDSRATIO;
ods output diffs=lsm_diff;
run;
```

If there is any convergence issues, then

For Non convergence, Wald test:

```
PROC FREQ DATA=<Imputed dataset> ORDER=DATA;
  Weight <Count>;
```

```
TABLES <treatment group>*<response variable>/riskdiff(equal var=NULL CI=wald) alpha=0.05;  
RUN;
```

Multiple Imputation

The number of imputations will be set to 500, the seed for the random function will be set to 4572322. The input data set should have one record per subject with Baseline PASI score as well as all change from Baseline PASI score.

To generate the multiple imputed data sets proc MI can be used as follows (example):

```
ODS LISTING CLOSE;  
ODS OUTPUT MissPattern=msgpat VarianceInfo=varinfo ParameterEstimates=param;  
PROC MI DATA=<pasi> OUT=<impdata> SEED=457<studycode> NIMPUTE=500;  
VAR <Baseline BMI> <age>  
    <Baseline PASI>  
    <change from baseline PASI week 16> - <change from baseline PASI week 52> PASI week primary endpoint  
BY <treatment group>;  
RUN;  
ODS LISTING;
```

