In order to also take strata and covariates into consideration a logistic regression model may also be performed for selected combinations of response distributions (e.g. worst case scenario where $J_1=0$ and $J_2=M_2$).

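### The supportive-analysis template in SAP 5.6.1.1 gives the odds ratio at covariate value 0 if it is used with an uncentred treatment-by-covariate interaction (minor correction)

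*SAP*

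**What the plan says.** **Template.** SAP 5.6.1.1, headed as supportive analysis, gives a PROC GENMOD block. Its class variables are a stratum and treatment, its explanatory variables are a placeholder, and its odds ratio comes from "ESTIMATE 'OR. AIN 300 mg VS. nb_UVB' <treatment> 1 -1/exp". It contains no centring step and names no covariate value.

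**Model it may serve.** SAP 2.5.4 repeats the Week 52 PASI 90 regression with treatment and all three of baseline PASI, age and BMI, and adds "Interaction terms with treatment also will be considered". The primary analysis (2.5.2) limits interactions to significant ones; 2.5.4 does not repeat that limit and gives no entry rule.

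**Other regressions nearby.**
- Non-responder imputation is a "supportive analysis of the primary variable using logistic regression (forward selection method) as described in primary analysis method".
- For LOCF, "Similar analysis will be performed using logistic regression (forward selection method) as described in primary analysis method".
- The first non-convergence step in 2.5.4 is "Run the PROC GENMOD procedure with EXACT statement". A later step replaces continuous BMI with a BMI stratum.
- SAP 5.6.1.2 (tipping point) says "a logistic regression model may also be performed for selected combinations of response distributions".

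**Primary code.** SAP 5.6.1 uses "lsmeans trt/diff cl exp ODDSRATIO", which by default evaluates the treatment difference at the covariate means.

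**Eligible range.** Protocol 6.4.1 requires "a PASI score of 10 or more at screening and baseline to be eligible for this study". Protocol 4.1 limits age to 18-50. BMI is in kg/m² (SAP 2.3.2.1).

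**The concern.** A contrast of 1 and -1 on treatment alone is the adjusted log odds ratio only when the treatment effect does not vary with a covariate, or when the covariate's zero is a sensible reference point. Here zero lies outside the study population for all three covariates. If an uncentred interaction were fitted, the output would carry the label of an ordinary drug-versus-nb-UVB odds ratio while reporting an extrapolation with a very wide confidence interval.

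At stake is the reading of one robustness check. A reader would naturally set this odds ratio beside the primary one. Depending on chance or on the direction of the interaction, a real effect could look absent, reversed or greatly inflated, when the two figures are simply different quantities.

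**Working it through.** **1. Planning figures.** SAP section 3 gives 70% versus 28%, 80 per arm, one-sided 0.025 and 99.9% power. The odds ratio is (0.70/0.30)/(0.28/0.72) = 6.00, log 1.792. Unpooled Wald: 0.42/√(0.70×0.30/80 + 0.28×0.72/80) = 5.86, and Φ(5.86 − 1.96) is above 99.99%, so the stated power is reproduced. The point does not depend on it.

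**2. Algebra.** With logit(p) = b0 + τ_i + b·x + g_i·x, the log odds ratio at x is (τ1 − τ2) + (g1 − g2)·x. The coded contrast returns τ1 − τ2, the value at x = 0. If x is replaced by x minus its mean, the same contrast returns the value at the mean.

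**3. Numerical check of the algebra.** Assume an odds ratio of 6.00 at mean BMI 28 and an interaction odds ratio of 0.95 per unit. The value at 0 is 6.00/0.95^28 = 25.2. One fit with N = 200,000 gave 24.4 for the uncentred contrast, under both reference and class-type coding, and 5.91 for the centred contrast, the same as the uncentred fit evaluated at mean BMI.

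For interaction odds ratios of 0.95 and 1.05 per unit, the value at 0 is:
- BMI (mean 28): 25.2 and 1.53
- age (mean 34): 34.3 and 1.14
- PASI (mean 18): 15.1 and 2.49

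**4. How often this would matter.** The documents give no covariate spreads, so these are assumed, as mean (SD). There are 4,000 simulated trials per scenario and no true interaction. The best single interaction enters only if its likelihood-ratio p is below 0.05; that rule is assumed too. PASI is kept at 10 or more and age within 18-50.

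| | PASI | Age | BMI | Enters | OR<1 given entry | OR<1, all trials | Reversed given entry | Reversed, all trials | Significant, all trials |
|---|---|---|---|---|---|---|---|---|---|
| A | 18 (7) | uniform | 27 (5) | 16.0% | 48.0% | 7.7% | 1.7% | 0.27% | 92.1% |
| B | 20 (10) | uniform | 28 (7) | 17.2% | 44.8% | 7.7% | 1.5% | 0.26% | 90.7% |
| C | 16 (5) | 32 (9) | 26 (4) | 16.0% | 55.2% | 8.8% | 3.1% | 0.50% | 91.1% |
| D | 15 (4) | 34 (9) | 27 (6) | 16.7% | 55.6% | 9.3% | 2.7% | 0.45% | 90.8% |
| E | 20 (7) | 38 (8) | 26 (4.5) | 16.3% | 48.6% | 7.9% | 3.5% | 0.57% | 91.9% |

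Reversed means significant in the wrong direction. The two columns headed all trials for OR<1 and Reversed are products, for example 16.0% × 48.0% = 7.7%. Given entry, 44-51% of trials are significant. At the covariate means, 99.9-100% of all trials are significant and, given entry, no odds ratio is below 1. Repeat runs of some scenarios put entry at 14-18%.

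**5. If an interaction is always fitted, with none true.** In a separate simulation (2,000 trials; means PASI 18, age 34, BMI 28), the standard error of the coded log odds ratio rises from 0.36 to 2.19 (BMI), 1.72 (age), 1.31 (PASI) or 3.07 (all three). Φ(1.792/SE − 1.96) gives 13%, 18%, 28% and 8%; the simulated values are 13%, 20%, 28% and 9%. Across scenarios A-E the ranges are 10-19% (BMI), 15-27% (age), 24-55% (PASI) and 7-11% (all three). At the means, significance stays at about 99.9%.

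**The case against.** **The code is a template, and its link to the sensitivity model is not established.** This stands. There is no cross-reference. The case for the link is that the block has no forward selection, whereas the non-responder and LOCF analyses both specify it, leaving the three-covariate model as the natural match. Against that, the block's stratum class variable has no counterpart in that model, and Arms A1 and B1 both lie in the naïve randomization stratum. A stratum fits the BMI-stratum non-convergence step, where a BMI of 0 has no meaning, or the optional tipping-point regression, for which no interaction is mentioned. The block has no EXACT statement, so it does not match the non-convergence step exactly either.

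**Several conditions must hold together.** This also stands. The block must serve this model, an interaction must be fitted, the covariate must be uncentred, and the programmer must leave the line unchanged. Under the assumed entry rule, 83-84% of trials with no true interaction never meet the second condition. An extreme odds ratio with a huge interval would also be noticeable.

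**Stronger readings a reader might infer.** One is that the contrast is wrong whenever an interaction is present. It is not: mean-centring makes it correct. Another is that the sensitivity analysis is bound to lose most of its power. The figures in step 5 require an interaction to be fitted every time, and 2.5.4 says only that interactions will be considered.

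What survives is the algebra, and the absence of a centring step or evaluation point in either section.

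**Conclusion.** The point holds conditionally, as a minor correction. If the 5.6.1.1 template is used for the Week 52 three-covariate model with an uncentred treatment interaction, its odds ratio is the effect at covariate value 0 and is not comparable with the primary estimate. Without an interaction, or with centred covariates, the code is right.

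The sizes rest on assumed covariate spreads and an assumed entry rule; the algebra rests on neither. Whether the defect ever reached an output cannot be told from the documents.

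A reader might infer that the primary conclusion is in doubt. The documents do not support that. The primary test uses LSMEANS, and the hierarchy in SAP 2.6.2 does not use this contrast. The forward-selection non-responder and LOCF analyses and the chi-square tipping-point analysis do not rest on it either. Only one non-confirmatory odds ratio is exposed.

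**What to change.** 1. In SAP 5.6.1.1, replace the ESTIMATE statement with `LSMEANS <treatment> / DIFF EXP CL;` and output the Diffs table instead of Estimates. Alternatively, centre baseline PASI, age and BMI at their pooled A1+B1 means before fitting. Neither changes the treatment odds ratio when no interaction is fitted.
2. Add to SAP 2.5.4: *If a treatment-by-covariate term is fitted, the odds ratio is reported at the pooled means of baseline PASI, age and BMI.* No new entry rule is needed.
3. Check the Week 52 sensitivity output. Only if it used `1 -1` with an uncentred interaction, re-run it and describe the correction in the final CSR. SAP 2.14.1 says a Week 52 report has already been prepared. The final CSR still covers the Main Study (2.1) and is where changes from the SAP are explained (section 1).

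The cost is two lines of code, one SAP sentence and a check of one output. Any re-run would be a documented post hoc correction of a supportive analysis and needs no new data.
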